23 7 days prior to completing their preliminary eligibility screening, (d) \leq 25 weeks pregnant, (e)
24 speak English, (f) own a smartphone (Android or iOS; 81.8% of pregnant women in wave 1
25 [2013-2014] of the Population Assessment of Tobacco and Health [PATH] reported owning a
26 smartphone). Exclusion criteria include: (a) current or prior mental or medical condition that
27 may interfere with study participation (assessed via self-report during formal intake assessment
28 completed online or by phone using a medical and psychosocial history questionnaire), (b)
29 smoke marijuana more than once each week and not willing to quit (marijuana smoking can
30 inflate breath CO), (c) exposed to unavoidable occupational sources of CO (e.g., car mechanic),
31 (d) report currently receiving opioid maintenance therapy (e.g., methadone, buprenorphine).
32 Women who meet the inclusion criteria and complete the informed consent process will be
33 considered formally enrolled and will be mailed equipment to participate in the study, but will
34 not be randomized until they (1) confirm receipt of their equipment, (2) complete an orientation
35 session on the smartphone app used in the current study (described subsequently), and (3)
36 provide a saliva sample indicating current smoking (i.e., test strip returns a positive for cotinine,
37 a metabolite of nicotine). Upon completing these steps, women will be randomized to either the
38 best practices plus incentives condition or best practices control condition (See Treatment
39 Conditions). The only criteria for withdrawing participants after randomization occurs will be
40 pregnancy termination or fetal demise.

41
42 **General Study Procedures.**

43 **Orientation Session:** After verifying eligibility and completing the informed consent process,
44 participants will be mailed two saliva test kits. Upon receiving the saliva tests, research staff will
45 aid participants in setting up their profile (e.g., create an account, upload profile photo) on the
46 DynamiCare smartphone application (“app”) which is used to submit breath and saliva samples

1 remotely. Participants will be trained in the operation of the app and will have the opportunity to
2 practice submitting saliva samples. The first sample that participants submit upon receiving their
3 saliva test kits will be used to validate smoking status and participants will be withdrawn prior to

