4 randomization if they are found to be non-smokers. Women who provide a baseline saliva test
5 validating that they are smokers will be randomized to one of the two treatment conditions, and
6 will be provided with information about that condition and a brief quiz (see attached) as part of
7 their orientation session. The orientation session will be conducted by telephone. Prior to the
8 orientation session, participants will be mailed a CO monitor, additional saliva cotinine test kits,
9 and an instruction manual containing general information about study procedures and where to
10 download the app that they will use during their participation, as well as specific information
11 about how frequently they should submit breath and saliva samples and a schedule of potential
12 earnings. Given that over 80% of pregnant women can be expected to own smartphones, these
13 women will use their existing phone during their participation to increase the ecological validity
14 of using a mobile phone to deliver the intervention. Women who do not own a smartphone but
15 have access to a computer with Internet access may pursue this option instead. We will collect
16 data on the number of participants who use mobile phones vs. computers to participate in the
17 intervention. During the orientation session, participants will also be informed that we will cover
18 the costs of study-related data transfer if they do not have unlimited data plans with their wireless
19 service provider. The purpose of this is to enhance the internal validity of this efficacy study by
20 reducing between subject variability in data coverage. We will also collect data on the number
21 of participants who require assistance paying for data coverage. Other details covered during
22 orientation include instructions specific to the condition to which participants are randomized
23 (e.g., schedule for submitting breath and saliva samples, the schedule of potential earnings, and
24 when the earnings commence). Researchers will read participants an information sheet specific
25 to their treatment assignment (attached), which will be followed by a brief quiz (attached). The
26 purpose of the quiz is simply to verify participant understanding of the condition to which they
27 are randomized. Participants will respond aloud to the quiz questions over the phone and any
28 incorrect answers will be discussed, and they will be invited to ask any additional questions upon

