29 completing the quiz. Participants will select a quit date during orientation (either the first
30 Monday following the call or the next Monday), and research staff will contact them by phone
31 on the Friday prior to their quit date. Staff will also inform participants to contact them in the
32 event that their phone is lost, stolen, or broken. In sum, participants who complete the informed
33 consent process will be mailed two saliva test kits to verify their smoking status prior to being
34 assigned to one of the two treatment conditions. Two tests will be sent in case participants' first
35 sample is invalid (e.g., insufficient saliva to produce a reading) and they need to complete a
36 second test to verify smoking status. Participants who are verified to be smokers will then
37 complete the treatment assignment phone call, after which study staff will provide them with the
38 equipment that they will need for the remainder of the study (e.g., breath CO monitor and
39 additional saliva test kits).

40
41 **Mobile-Phone Based Financial Incentives:** The intervention will be delivered on participants'
42 smartphones via an app installed on their phone either before or during the orientation session.
43 The process of submitting a video entails the following steps: (1) Participant opens the app,
44 which requires them to type in a password. Their username and password (stored as a secure,
45 “irreversible” one-way hash) will be stored in a configuration file accessible only to the
46 application; (2) The app will verify the password and participants will be taken to the “home”

1 screen which will show their cumulative earnings to date and a “post video” button; (3) The app
2 will attempt to contact the server over the Internet (via a 3G/4G mobile network) to determine
3 the correct time and status of the participant; (4) The participant will click on the post video
4 button, thereby leading them to a simple interface for recording videos that contains a start/stop
5 recording toggle button, a play button to review the recorded video, and a post button to send the
6 video to the server; (5) After posting the video, the server will display a voucher based on the
7 voucher schedule cached from the prior video upload. The app will then create a text file
8 containing a timestamp and video file. These files will be archived, compressed, and encrypted
9 to prevent tampering and/or eavesdropping while in transit. The app will maintain a file lock on

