1 research staff meetings. Any SAE will be brought to the attention of the PI as soon as possible
2 and not longer than 24 hours. Any AE or SAE that is both unexpected and related to the study
3 participation will be reported to the IRB within 7 days of the event. That IRB will make a
4 determination as to whether additional reporting requirements are needed. IRB actions will be
5 reported to the funding agency by the PI no less than annually and more frequently as
6 recommended by the local IRB. Any SAEs will be summarized in the yearly Progress Reports to
7 the funding agency, including a review of frequency and severity. All SAEs will be followed
8 through ongoing consultation with the physician caring for the patient until they resolve, result in
9 death, or stabilize and are not expected to improve.

10

11 **Withdrawal Procedures**

12 Women will be free to withdraw at any point during the course of the study without penalty.
13 That will be explained during informed consent. In terms of data analysis, we will adhere to an
14 intent-to-treat approach (Armitage, 1983) wherein all women randomized to the study conditions
15 will be included in the analyses independent of early dropout, noncompliance, etc., with the
16 exception of excluding women for abortion/fetal demise prior to their late pregnancy smoking
17 assessment. Women who receive their equipment and fail to complete an orientation session, as
18 well as women who provide a baseline CO sample indicating that they are non-smokers, will be
19 withdrawn prior to randomization and thus not included in an intent-to-treat analysis.

20

21 **Sources of Materials**

22 The research materials to be obtained include interviews, questionnaires, and breath and saliva
23 specimens to verify smoking status (and serve as the basis for reinforcement in the incentives
24 condition). Materials will be collected remotely using a combination of phone calls with
25 participants, online surveys, and remote video capture via smartphone app (i.e., for submission of
26 breath CO samples and salivary cotinine samples). These data will be entered into databases with
27 no identifying information (i.e., with subject ID only). These databases are stored on password-
28 protected external hard drives in locked offices in a locked clinic accessible only to the PI and
29 research staff.

30

31 **SUBJECT CHARACTERISTICS, IDENTIFICATION AND RECRUITMENT**

32

33 **Subject Selection**

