20 currently maintained on opioid maintenance therapy. The only criteria for withdrawing someone
21 from the trial following randomization to treatment condition will be pregnancy termination or
22 fetal demise prior to participants' late-pregnancy smoking assessment (≥ 28 weeks gestation).
23 Women who fail to complete an orientation session or provide an initial CO sample indicating
24 that they are smokers will be withdrawn prior to randomization. Criteria will be assessed during
25 an initial eligibility screen that can be conducted either online or by phone to determine
26 preliminary eligibility and further evaluated during the formal intake assessment.
27

28 **Inclusion of Minorities and Women**

29 This project will include only women. Smoking among pregnant and newly postpartum women
30 has sufficiently special circumstances regarding the potential toxicity to the fetus and newborn,
31 the reasons for trying to quit smoking and prevent relapse, and the patterns of smoking reduction,
32 cessation, and relapse that they need to be studied exclusively in women.
33

34 Additionally, the project will include only Alaska Native women. However, should we receive
35 referrals from non-Alaska Native women in Alaska who are pregnant and currently smoking, we
36 will refer them to the Alaska tobacco quit line.
37

38 **Recruitment**

39 As in prior and current trials conducted at UVM, including the ongoing parent trial, applicants
40 will be recruited from online media advertisements. The text for these ads, as well as exemplars
41 of pictures, are attached to this submission. These ads were developed based on prior research
42 conducted by the ANTHC involving online recruitment of Alaska Native women. These ads will
43 include a link to the preliminary screening questions administered through REDCap. If eligible,
44 we will collect the participant's contact information and schedule a time to contact them to
45 provide more information about the study and conduct the consent phone call if they choose to
46 enroll.

1
2
3
4

FINANCIAL CONSIDERATIONS

5

Expense to Subject

6 No known expense to subject aside from their time.
7

8

Payment for Participation

9 Women in both conditions will receive compensation for completing 7 formal assessments at
10 \$50/assessment = \$350. Women assigned to the best practices plus incentives condition will
11 have the potential to earn incentives in the form of money loaded onto a PEX Debit Card for

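### The orientation session lies on both sides of randomisation, so the plan gives two answers on whether a woman who leaves it after hearing her arm belongs in the intent-to-treat set

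*Combined protocol and SAP*

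**What the plan says.** All sections cited are in the combined protocol and SAP.

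- **Procedures, Participants.** Enrolled women will "not be randomized until they (1) confirm receipt of their equipment, (2) complete an orientation" session on the app and give a saliva sample that is positive for cotinine. The only grounds for withdrawal after randomisation are pregnancy termination or fetal demise.
- **General Study Procedures, Orientation Session.** Women with a baseline saliva test "validating that they are smokers will be randomized to one of the two treatment conditions, and" they "will be provided with information about that condition and a brief quiz (see attached) as part of" the orientation session. Other details covered in "orientation include instructions specific to the condition to which participants are randomized", such as the sampling and earnings schedules. After the quiz comes the quit date: "completing the quiz. Participants will select a quit date during orientation (either the first" or the second Monday). The closing summary of this section also mentions a treatment assignment call that follows smoking verification, without saying whether it is the same session.
- **Data Safety and Monitoring, Withdrawal Procedures.** One sentence analyses all randomised women regardless of early dropout, except after abortion or fetal demise before the late-pregnancy assessment. The next removes women who "Women who receive their equipment and fail to complete an orientation session, as" well as baseline non-smokers, and calls them "withdrawn prior to randomization and thus not included in an intent-to-treat analysis".
- **Inclusion/Exclusion Criteria.** "Women who fail to complete an orientation session or provide an initial CO sample indicating" smoking are withdrawn before randomisation. This section does not mention intent-to-treat. The sentence before it repeats that fetal loss is the only reason for withdrawal after randomisation.
- **Statistical Methods.** The intent-to-treat rule for all randomised women is repeated.

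**The concern.** A session with arm-specific content cannot be finished before an arm has been assigned. The condition in Participants and the sequence in Orientation Session therefore cannot both be followed as written. That would be a matter of housekeeping, except that completion of this session is also the test Withdrawal Procedures uses to decide who is left out of the analysis.

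The two arms are offered different things, and the woman learns which is hers during this session. The incentives arm can earn up to $1,620 on top of the $350 for assessments that both arms receive, and it also carries the sampling burden. Leaving could plausibly depend on the arm. An exclusion that follows allocation and can depend on it undoes the protection of randomisation. Staff could apply the withdrawal sentence literally and believe that they were following the protocol.

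**Working it through.** **1. The rules applied to one case.** Take a woman whose saliva test is positive, who is randomised and told her arm, and who ends the call before the quiz or the quit date.

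| Rule | Her status | In the intent-to-treat set? |
|---|---|---|
| Statistical Methods; first rule in Withdrawal Procedures | Randomised, early dropout | Yes |
| Participants; Inclusion/Exclusion Criteria (fetal loss the only reason for withdrawal after randomisation) | Not withdrawn | Yes |
| Second rule in Withdrawal Procedures | Did not complete orientation, so classed as withdrawn before randomisation | No |
| Non-completion rule in Inclusion/Exclusion Criteria | Did not complete orientation, so classed as withdrawn before randomisation | Not stated |

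Receipt of equipment does not settle the timing. The Orientation Session section has the CO monitor and extra kits mailed before the session in one place and provided after the assignment call in another.

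**2. Size.** The plan gives no figure on this point, so there is nothing to reproduce. The following is an illustration.

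Inputs from the plan: 30 women per arm; pilot late-pregnancy quit rates of about 37% and 11%; a Cochran-Mantel-Haenszel (CMH) test; alpha 0.05.

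Assumptions: two-sided test, one stratum, no continuity correction; the number of leavers; and that each leaver would have counted as a smoker. The plan's rule that missed samples are positive concerns incentive samples, so it does not establish the last of these for formal assessments.

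With a of n1 abstinent on incentives, b of n2 abstinent on control, N = n1 + n2 and m = a + b:

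CMH statistic = (a − n1·m/N)² ÷ [n1·n2·m·(N − m) / (N²(N − 1))]

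The table closest to the pilot is 11/30 versus 3/30, which is 36.7% versus 10.0%:

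- numerator: (11 − 30 × 14/60)² = 4² = 16
- variance: 30 × 30 × 14 × 46 / (3,600 × 59) = 2.729
- statistic: 16 / 2.729 = 5.86, p = 0.016

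Removing smokers from one arm changes only that arm's denominator:

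| Table | Change | Difference (points) | CMH p | Uncorrected chi-square p |
|---|---|---|---|---|
| 11/30 v 3/30 | none | 26.7 | 0.016 | 0.015 |
| 11/27 v 3/30 | 3 dropped, incentives | 30.7 | 0.008 | 0.007 |
| 11/30 v 3/27 | 3 dropped, control | 25.6 | 0.027 | 0.025 |
| 11/30 v 3/24 | 6 dropped, control | 24.2 | 0.046 | 0.044 |

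Tables chosen because they lie near 0.05:

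| Table | Change | Difference (points) | CMH p | Uncorrected chi-square p |
|---|---|---|---|---|
| 9/30 v 3/30 | none | 20.0 | 0.055 | 0.053 |
| 9/28 v 3/30 | 2 dropped, incentives | 22.1 | 0.039 | 0.038 |
| 10/30 v 3/30 | none | 23.3 | 0.030 | 0.028 |
| 10/30 v 3/26 | 4 dropped, control | 21.8 | 0.056 | 0.054 |

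Under the smoker assumption, exclusions from the incentives arm enlarge the effect and exclusions from control shrink it.

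**The case against.** The sponsor has a good reply. Both withdrawal sentences say that the women are withdrawn before randomisation, and a woman who holds an allocation cannot be. The intent-to-treat rule and the single permitted reason for withdrawal after randomisation are each stated more than once. Read together, they make someone who hangs up after hearing her arm an early dropout who stays in. The condition in Participants concerns a session on the app, which suggests training only, and the mention of an assignment call suggests that two steps were intended. The quiz is described only as a check of understanding, and no text makes the quiz or the quit date the test of having completed orientation. Consent also covers both conditions and the equal chance of each, so assignment to control is not news in the middle of the call.

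Most of this stands, and it limits the point. A reader might infer that the plan sets out to remove randomised women from the analysis; the documents do not support that. What the reply does not do is remove the conflict. The reference to timing describes what happens to non-completers. It does not restrict who counts as one, and it relies on the order in Participants that the Orientation Session section contradicts. The exclusion is keyed to the orientation session, which is the same term that section uses for the steps after assignment.

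**Conclusion.** The contradiction holds and should be resolved. For a woman allocated during the session who does not finish it, the wording supports both inclusion and exclusion, and no sentence gives one rule precedence.

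The likely size is modest and cannot be estimated from the documents. They do not say how many women might leave at this step or from which arm, so the direction of bias is open. At the pilot-like result, three exclusions from one arm shift the estimate by about 4 points upward (incentives) or 1 point downward (control). A reader might infer from the borderline tables that the trial's conclusion hangs on this. It does not: the pilot-like result stays below 0.05 even with six controls dropped. The shift in the estimate still has some weight, because the results are meant to inform sample-size calculations for larger studies.

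**What to change.** 1. In Participants and Orientation Session, define a step before randomisation (app training and smoking verification) and a separate assignment call after it (condition information, quiz, quit date). Use a different name for each.
2. In Withdrawal Procedures and Inclusion/Exclusion Criteria, limit the exclusion to women who do not complete the first step before an allocation is generated.
3. State that every woman for whom an allocation has been generated stays in the intent-to-treat set whether or not she finishes the assignment call, apart from the fetal-loss exception already stated.
4. Report the number of women leaving at each step, by arm once allocated.

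The same edit should reconcile two related differences: when the equipment is sent, and the baseline smoking check, which is a saliva test in Participants and Orientation Session but a CO sample in the two withdrawal sentences.

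The cost is wording only. A few women who leave immediately after assignment stay in the denominator, which may lower quit rates slightly.
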